#### 7.0 Setting

There will be one study site, the Medical University of South Carolina Kidney Transplant Center. The MUSC IRB will review and approve the study and protocol. Patients will be screened, approached, consented, and randomized prior to discharge from the hospital for their kidney transplant event on 6E or during a routine clinic appointment (9th floor RT) as long as it is within 7 days of transplant.

#### 8.0 Recruitment Methods

Each weekday, the study coordinator will review the kidney transplant roster to determine new patients that received a transplant within the past 24 to 72 hours. The coordinator will screen each patient to determine if they meet inclusion and exclusion criteria and review with the study team prior to approaching for consent.

#### 9.0 Consent Process

Patients that are screened and meet criteria will be approached by study personnel for informed consent within 7 days of kidney transplantation. This may occur during the index hospitalization for the transplant or during a routine clinic follow-up in the ambulatory care setting. The MUSC IRB approved consent form will be reviewed with each patient. The study rationale and all study-related interventions and procedures will be reviewed with the potential participant. All questions will be answered, and patients will be given adequate time to review the information, including the consent documentation. Participation is completely voluntary, and patients will be informed of the usual process should they not care to be involved in this study.

Persons that have impaired decision making may be included in this study. These patients will be provided with the same information provided all patients, but this information will be discussed in detail with both the patient and their legal representative that has the authority to make medical decisions for the patient.

#### 10.0 Study Design / Methods

This will be a 12-month, single-center, open-label, randomized controlled clinical trial enrolling 70 total patients (35 in each arm). Given the limited sample size and single center design, this is a small, exploratory trial with limited power to detect significant differences between treatment arms for rates of CMV infection and other clinical endpoints (acute rejection, graft loss, death). The study is powered to detect clinically meaningful and statistically significant differences in the incidence of leukopenia accompanied by a reduce in total mycophenolate dose or valganciclovir dose (see power/sample size section). Patients will be randomly assigned to receive valganciclovir

900mg PO daily (this is considered standard usual care, adjusted for renal function) for 3-6 months post-transplant (based on CMV D/R serostatus as detailed below) or maribavir 400mg PO BID for 3-6 months post-transplant (based on CMV D/R serostatus as detailed below) + acyclovir 400mg PO BID for 1-month post-transplant (investigation arm, the addition of acyclovir to maribavir is considered standard usual care for HSV prophylaxis). Patients that are D+/R- will receive 6 months of prophylaxis, while all other CMV serostatuses will receive 3 months of prophylactic therapy (per MUSC usual care CMV protocol). All other medications, including immunosuppression and additional anti-infective prophylaxis, will be per standard usual care. All follow-up laboratory assessments and clinic visits will occur as per usual care as well. The only additional procedure specific to this study is that patients will be self-administered two surveys at 3, 6, and 12-months post-transplant, which can be completed online during a routine clinic visit or at home. There will be no visits conducted solely for this research study.

Data collection will be as follows: Baseline data will include sociodemographics, comorbidities, serologies, donor information and transplant characteristics. Follow-up data will include induction therapy, immunosuppression type, dosing and levels, laboratory data, biopsy pathology reports, infection type and severity, hospitalizations and cause, ED visits and cause, allograft function, graft loss and death. All data will be gathered in a comprehensive manner using both electronic and manual chart abstraction. There are no study-specific procedures that will be conducted. All follow-up data that is accessible in the MUSC electronic medical record (EMR) will be gathered, curated, aggregated, and analyzed. Both MUSC and external non-MUSC labs are entered into the EMR. All acute rejections are confirmed by biopsy and pathology reports available in the EMR. All graft loss and death events are also documented in the EMR. Clinically significant infections, particularly CMV, are also well-documented in the MUSC EMR. Hospitalizations and ED visit within MUSC will be captured; however, non-MUSC outside hospitalizations and ED visits will not be accessible for this study. Below is a table outlining key follow-up time periods and data elements collected during these times.

Assessments		Pre-transplant	Day Post-transplant							Week Post-Txp		Month Post-transplant		
Time Frame			1	2	3	4	5	6	7	2	4	3	6	12
RANDOMIZATION			X											
History and Physical 		X							X		X	X	X	X
Vital Signs		X	X			X			X	X	X	X	X	X
Serologies 		X												
Laboratory Assessment	CBC and BMP	X	X			X			X	X	X	X	X	X
	Tacrolimus levels				X				X	X	X	X	X	X
CMV Infection Assessment									X		X	X	X	X
Clinical assessment 									X	X	X	X	X	X
HRQOL PROMIS Survey												X	X	X
QualityMetric Patient Satisfaction Survey												X	X	X

Foot notes:

1. Within 48 hours of transplant
2. Includes testing for CMV, Epstein-Barr, hepatitis B & C and HIV for donor and recipients
3. Includes assessments of adverse events, antiviral drug doses, allograft rejection, infection, need for dialysis, hospitalization, ED visits, graft loss, and all immunosuppressant medications and doses

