### 3.0 Intervention

Patients will be randomized to receive either maribavir 400mg PO BID or valganciclovir 900mg daily (standard of care dose, adjusted for renal function) for CMV prophylaxis for 3 to 6 months post-transplant. Those that are CMV serostatus D+/R- will receive 6 months of antiviral therapy; all others will receive 3-months of therapy. The current gold-standard therapy is valganciclovir for 3- to 6-months of therapy. Those randomized to maribavir will also receive 1-month of acyclovir 400mg PO BID for HSV prophylaxis (standard of care dose). Beyond these interventions, all follow-up care and laboratory monitoring will be conducted as per usual care protocols. All immunosuppression will be given and dosed as per usual care protocols. There will be no additional visits or laboratory measurements as part of this study.

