### 4.0 Study Endpoints

#### Safety Measures

1. Leukopenia with an accompanying dose reduction (Primary Outcome) – Defined as a total WBC count of  $< 3,000$  cells/mm^3 with a reduction in the total daily dose of mycophenolate below 1500mg per day or valganciclovir below 900mg daily (adjusted for renal function). This will be assessed as a dichotomous outcome (yes/no) per patient as well as a rate (number of unique leukopenia events per patient-year). Events will be considered unique once the WBC count recovers to normal range on two consecutive measures. The length of time a patient has leukopenia, and the severity of leukopenia (nadir WBC) will also be assessed. This endpoint will be measured at 3-, 6-, and 12-months post-transplant.

2. Neutropenia (Secondary Outcome) – Defined as an absolute neutrophil count of  $<1,000$  cells/mm^3. This will be assessed as a dichotomous outcome (yes/no) per patient as well as a rate (number of unique neutropenic events per patient-year). Events will be considered unique once the neutrophil count recovers to normal range on two consecutive measures while not receiving G-CSF therapy. The length of time a patient has neutropenia, and the severity of leukopenia (nadir WBC) will also be assessed. This endpoint will be measures at 3-, 6-, and 12-months post-transplant.
3. Mycophenolate mofetil dose reduction (Secondary Outcome) – Defined as a reduction in dose of  $<1,500$  mg per day ( $<750$  mg PO BID). This will be assessed as a dichotomous outcome (yes/no) per patient as well as a rate (number of unique mycophenolate dose reduction events per patient-year). Events will be considered unique once the mycophenolate dose is returned to full dose for at least one week. The length of time a patient has their mycophenolate dose  $<1,500$  mg per day and the severity of mycophenolate dose reduction (nadir dose) will also be assessed. This endpoint will be measures at 3-, 6-, and 12-months post-transplant.

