### **Power/Sample Size**

This study is adequately powered to detect a clinically meaningful and statistically significant difference in the incidence of clinically significant leukopenia in those randomized to maribavir vs. valganciclovir under most incident rate scenarios. For this study, clinically significant leukopenia is defined as a WBC count of <3,000 AND a reduction in the dose of mycophenolate or valganciclovir dose. Based on a retrospective analysis of internal data, the expected incidence of clinically significant leukopenia in the valganciclovir arm is between 33 and 35%. To support this incident rate, we conducted a retrospective analysis of our internal data to fully assess the incidence of clinically significant leukopenia. In this analysis, we included 446 adult kidney transplant recipients transplanted at MUSC between 2007 and 2015. We chose this time period as we had comprehensive data on induction, WBC counts, and MMF dosing to allow for assessment of the incidence of clinically significant leukopenia. Of these patients, 127 (28%) received rATG induction. The incidence of WBC <3K with and without MMF dose reduction is detailed in the table below, which was assessed within 1 year of transplant. This data matches our expected incidence of leukopenia in the VGC arm of 35%. This is because patients in the proposed study will be receiving rATG or be CMV D+/R- and receive 6-months of VCG/maribavir and be at higher risk of leukopenia.

[figure not shown]
Induction Agent	N	WBC <3K	WBC <3K and MMF Dose Reduction
Basiliximab	319	36.7%	21.3%
rATG	127	56.7%	34.6%

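### The open-label primary endpoint needs a dose cut and gives the valganciclovir arm an extra route to an event, and no listed endpoint counts WBC <3,000 alone

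*Combined protocol and SAP*

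**What the plan says.** Section 10.0 describes a "single-center, open-label, randomized controlled clinical trial". In Section 4.0, item 1 is "Leukopenia with an accompanying dose reduction (Primary Outcome"): a WBC below 3,000 cells/mm³ "with a reduction in the total daily dose of mycophenolate below 1500mg per day or valganciclovir below 900mg daily (adjusted for renal function"). Hypothesis 1 and the Power/Sample Size section also require the dose condition. Section 3.0 adds: "All immunosuppression will be given and dosed as per usual care protocols". The supplied text contains no rule linking WBC to dose and no blinded adjudication of the endpoint.

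Several related measures are planned:
- Item 1 continues: "The length of time a patient has leukopenia, and the severity of leukopenia (nadir WBC) will also be assessed".
- Item 2, neutropenia, is laboratory-only: "Defined as an absolute neutrophil count of" less than 1,000 cells/mm³, as yes/no and as a rate.
- Item 3 is "Mycophenolate mofetil dose reduction (Secondary Outcome"), with no WBC condition. Items 4 and 5 do the same for valganciclovir and for either prophylaxis drug.

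The Statistical Methods section lists leukopenia incidence among the outcomes for chi-square or Fisher testing, but does not say whether the dose condition applies.

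For the planning cohort, both forms are tabulated: "The incidence of WBC <3K with and without MMF dose reduction is detailed in the table below".

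**The concern.** A low count becomes a primary event only if someone who knows the assignment lowers a dose. The plan records an expectation in favour of maribavir: the sample-size rationale says it does not seem to cause or worsen leukopenia, and Section 16.0 anticipates less leukopenia leading to dose reductions. Section 2.0 describes how, on valganciclovir, an unexplained low count prompts reduction of either drug. A different readiness to cut doses between arms is therefore foreseeable.

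The definition adds an imbalance that does not depend on anyone's expectations. A leukopenic patient on valganciclovir can qualify through mycophenolate or through valganciclovir. A leukopenic patient on maribavir can, as assigned, qualify only through mycophenolate, because a maribavir reduction does not count.

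Aim 1 is stated in terms of the incidence of leukopenia. If the composite differs, readers will ask whether the blood counts differed, and no listed endpoint answers that at the primary endpoint's own threshold.

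**Working it through.** **The plan's own figure.** The plan states 32 per arm for at least 80% power at 33–35% vs 5–6% (two-sided 0.05, chi-square). At 33% vs 6% the pooled Pearson formula gives 33 per arm, and a power of 0.792 at 32 per arm. The likelihood-ratio chi-square formula gives 0.809 at N = 64, which is the tabulated value. The sample size is reproduced and is not in question here.

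**Inputs from the planning table (Power/Sample Size).**

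| Induction | n | WBC <3K | WBC <3K and MMF cut | Cut fraction |
|---|---|---|---|---|
| rATG | 127 | 56.7% | 34.6% | 34.6/56.7 = 61% |
| Basiliximab | 319 | 36.7% | 21.3% | 21.3/36.7 = 58% |

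About four in ten leukopenic patients had no MMF cut and would not have counted. The table covers MMF cuts only, so these fractions exclude valganciclovir reductions.

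**Check 1: same counts, different prescribing.** Composite rate = P(WBC <3,000) × cut fraction. Set P(WBC <3,000) = 56.7% in both arms and the valganciclovir cut fraction to 61%, giving 34.6%. The maribavir cut fractions are assumptions. The last column is the exact probability that a two-sided Pearson test at 35 per arm gives p<0.05.

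| Maribavir cut fraction (assumed) | Composite on maribavir | P(p<0.05) |
|---|---|---|
| 61% (equal) | 34.6% | 0.05 |
| 40% | 0.567 × 0.40 = 22.7% | 0.195 |
| 30% | 0.567 × 0.30 = 17.0% | 0.387 |
| 20% | 0.567 × 0.20 = 11.3% | 0.651 |

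In the last three rows nearly all of the significant results favour maribavir.

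**Check 2: how far prescribing alone could go.** To reach the planned 5% with unchanged counts, the maribavir cut fraction would have to be 0.05/0.567 = 8.8%, against 61% in the other arm.

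**Check 3: asymmetry alone.** Keep counts and mycophenolate cutting equal. Assume that half of the leukopenic valganciclovir patients without an MMF cut have valganciclovir reduced. The composite there is 34.6 + (56.7 − 34.6)/2 = 45.6%, against 34.6% on maribavir, and p<0.05 occurs in about 15% of trials.

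**Check 4: would a count-only outcome be informative at this size?** With 56.7% on valganciclovir and 35 per arm, power by the Pearson formula is 0.90 if the maribavir rate is 20%, 0.81 at 24%, 0.62 at 30% and 0.39 at 36.7%. The documents give no maribavir rate for WBC <3,000, so these rates are assumptions.

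**The case against.** The composite is deliberate. Section 2.0 presents dose reductions as part of the burden of leukopenia, and the hypothesis concerns leukopenia that is clinically meaningful in that sense. The plan is also not blind to the components. If counts were identical and only prescribing differed, nadir WBC and ANC <1,000 should look similar while items 3 to 5 diverge. A nadir below 3,000 is in effect the missing yes/no variable, and the unqualified leukopenia incidence in Statistical Methods might be meant as that count. Dosing follows usual-care protocols, and the Appendix that Section 4.0 cites is not in the supplied text, so a dose rule may exist there. The cut fractions in Check 1 have no source in the documents, and the 61% comes from rATG patients transplanted in 2007–2015, whereas D+/R- patients without rATG are also eligible.

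Most of this stands, and it limits the point. A reader might infer that an effect on leukopenia could not be told apart from prescribing behaviour at all. The documents do not support that, because the planned laboratory and dose endpoints allow a partial separation. A reader might also infer that the whole planned effect could be a prescribing artefact, but Check 2 shows how extreme that would have to be. Nor does the 61% mean that only the other 39% turn on a decision: every composite event requires a cut.

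The gap remains. ANC <1,000 is a different cell count and threshold. Nadir and duration sit inside the composite's item, with no statement that they cover patients who do not meet it. The leukopenia entry in Statistical Methods is undefined. The asymmetry stands whatever the usual-care protocol says. A WBC-only outcome is imperfect too, since later counts can be altered by dose changes or G-CSF and CBC timing follows usual care. It supports the composite and does not replace it.

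**Conclusion.** The concern holds as one of bias and interpretability. The primary endpoint depends on dose decisions made with knowledge of the arm and favours maribavir by construction through the valganciclovir-only component. The yes/no count of WBC <3,000 that the plan tabulates for its own planning cohort is not a listed endpoint.

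Under the assumed cut fractions, identical counts give p<0.05 in about 20% to 65% of trials instead of about 5%. These figures illustrate sensitivity and do not forecast this trial. They rest on the historical rATG rate applying to both arms and on cut fractions that the documents do not supply. A moderate prescribing difference could mislead the primary test, but it would take an extreme one to produce the whole planned difference.

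**What to change.** Keep the composite as the primary endpoint and amend Section 4.0 and Statistical Methods as follows:
1. Name any WBC <3,000 cells/mm³, irrespective of dose change, as the first secondary outcome in all randomised and treated patients. Report the risk difference and 95% CI beside the primary result.
2. State that nadir WBC and duration of leukopenia are analysed in all such patients, not only in those meeting the composite.
3. Report the primary result by component: events with a mycophenolate cut, and events with a valganciclovir cut.
4. Say in Statistical Methods whether the listed leukopenia incidence carries the dose condition.
5. State that the primary result will be interpreted in the light of these, noting that later counts can reflect dose changes or G-CSF.

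The cost is SAP wording. CBCs and doses are already collected and the sample size need not change. The downside is that a primary result not supported by the counts would have to be stated more cautiously. Adding the outcome once results are known would forfeit the value of prespecifying it.

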### **Statistical Methods**

The analyses to assess for study Aims will be conducted using standard and widely accepted statistical methods. Data will be reported using percentages for nominal variables and univariate comparisons using Fisher's exact test or Pearson's chi-squared test as appropriate. This includes baseline demographics and transplant characteristics, as well as the non-time to event outcome

variables. For continuous variables with normal distribution, results will be reported using means and standard deviations with univariate statistical comparison using Student's t-test for two independent samples. For non-normally distributed variables, data will be reported using medians and interquartile ranges, with univariate statistical comparison conducted using the Mann Whitney U test. Normal distribution of continuous variables will be assessed using normality plots and the Shapiro-Wilk test. Normal variance will be assessed using Levene's test for equality of variances. Chi square or Fisher's exact test will be used for univariate assessments of key outcomes, including the incidence of leukopenia, neutropenia, CMV antiviral prophylaxis dosing interruption, CMV infection, acute rejection, graft loss and death.

If necessary, multivariable analysis assessments for Aims 1 and 2 will be conducted using Cox regression time to event models. The primary variable of interest in these models will be treatment (maribavir vs. valganciclovir). If necessary and appropriate given event rates, Cox regression analysis will also be used for survival analyses involving all time to event outcomes, including time to acute rejection, time to graft loss and time to death. Models will be adjusted for key variables known to influence outcomes, including CMV serostatus and rATG induction. To prevent overfitting, no more than one covariate for every 5 events will be included in these models. Given the small sample size and expected event rates, Cox models will likely be overfit if including >2 covariates plus the primary treatment variable. Thus, multivariable modeling will be limited to only include key baseline variables that are known to influence the risk of CMV infection and that significantly differ by treatment arm based on preliminary univariate analyses; this will most likely only include CMV D+/R- serostatus and/or rATG induction. Prior to conducting Cox regression, modeling assumptions will be assessed, including proportionality of hazards across treatment arms and assessing the optimal functional forms of non-dichotomous covariates.

For Aim 3, total hospital charges and healthcare utilization will be modeled using a validated method we have used in previous studies. This will be a two-part statistical models for zero-heavy continuous data. The general format of the suggested model in which we fit a logistic model for the probability of non-zero response and a conditional generalized linear model (GLM) for the mean response given that it is non-zero. We will consider several distributions for the GLM part (eg, log-normal, gamma and Weibull, zero-inflated negative binomial [ZINB]) and the best fitting model will be selected using Bayesian information criterion (BIC). Parameter estimates of percent change in total hospital charge per unit increase in the values of each covariate in the model and their 95% CI will be computed using SAS Proc FMM.

For Aim 4, survey results will be aggregated using validated methods for each survey. The mean scores will be compared between treatment arms, as well as the mean change across the three measurement timepoints. Comparisons will be made using standard statistical tests based on the distribution of the results (Student's t-test for normal variance or the Mann-Whitney test for non-normally distributed data). Mean change will be assessed using general linear modeling (GLM) for repeated measures data with the appropriate link based on the distribution of the measures.

For Aim 5, interaction terms will be added to multivariable models (Cox regression or GLM) to assess if there are differences by race (race\*treatment) or sex (sex\*treatment). A p-value of <0.1 will be considered sufficient evidence of likely effect modification and the analysis will then be stratified by the appropriate variable (either race or sex) for a given outcome if there is in fact a significant interaction. Given the limited sample size, there is likely low power to detect statistically significant differences for this Aim; thus Aim 5 is considered exploratory in nature.

We will also assess for any impact of maribavir on tacrolimus dosing or trough concentrations. Steady-state stable doses of tacrolimus (mg/day) and whole blood trough concentrations will be assessed and compared in patients during maribavir therapy versus after completion of therapy. Changes will be compared between the treatment arms using difference in difference methodology to assess for drug-drug interactions. The level-normalized dose (dose needed to achieve a level of 8 ng/mL using linear proportions) will also be compared using difference-in-difference analysis. Finally, the proportion of patients in the maribavir arm that have more than a 10% change in level-normalized dose after discontinuing maribavir therapy will be collected and reported. These analyses are considered exploratory.

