### 3. Recipient of investigational, non-FDA approved medication

#### 6.0 Number of Subjects

70 patients will be randomized 1:1 (35 in each arm) in blocks of 10. Once a patient is randomized and receives at least one dose of CMV prophylaxis medication they will be included in the study in an intent-to-treat manner. Those that are lost to follow-up, withdraw, or are taken off study drug will not be replaced.

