The incidence of clinically significant leukopenia (WBC <3K AND dose reduction in MMF) is difficult to assess in the maribavir arm, as this specific issue is not reported in the published data. However, there are several studies that can be used to estimate this incidence for power/sample size purposes. In a study conducted in liver transplant patients, known to be at higher risk for cytopenias than kidney recipients, the incidence of neutropenia was 6% in the maribavir arm (Winston DJ et al Am J Transplant 2012;12:3021-30.). In a phase III prophylaxis study in allogeneic stem-cell transplants, who are very high risk for cytopenias, the incidence of neutropenia was similar between the maribavir, and placebo arms and the average WBC count was 4.2K in the placebo arm and 4.4K in the maribavir arm (Papanicolaou GA et al. Clin Inf Diseases 2019;68:1255-64.). Thus, maribavir does not appear to induce or worsen leukopenia and a 5% incidence is a reasonable expectation in the maribavir treatment arm for estimating sample size and power.

To meet at least 80% power, given an incident rate of 33 to 35% in the valganciclovir arm and 5 to 6% in the maribavir arm, 32 patients in each arm is required, assuming two independent samples, a two sided  $\alpha=0.05$ , and using the chi square test. This sample-size will be inflated to 35 patients per arm to address an expected dropout/lost to follow-up rate of 3-5% in each arm. Thus, 70 total patients, 35 in each arm, will provide adequate power to assess the primary aim of this study. SAS 9.4 (SAS Institute, Cary, NC) was utilized to conduct sample-size estimations (Proc Power).

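### With about 2 primary events expected in the maribavir arm, the adjusted Cox model for Aim 1 needs an inference method that works when that arm has few or no events

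*Combined protocol and SAP*

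**What the plan says.** The unadjusted comparison of leukopenia incidence uses a chi-square or Fisher's exact test (section 10.0, Statistical Methods). The adjusted analysis follows: "If necessary, multivariable analysis assessments for Aims 1 and 2 will be conducted using Cox regression time to event models". Treatment is the variable of interest in these models. CMV serostatus and rATG induction are the likely covariates.

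The plan recognises that events will be sparse, but only as a question of how many covariates to allow. It permits one covariate for every 5 events and warns that "Cox models will likely be overfit if including >2 covariates plus the primary treatment variable". It does not say whether treatment will be judged by a Wald, score or likelihood-ratio test, how confidence limits will be formed, or what happens if one arm has no events.

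The planning figures are in Power/Sample Size: "given an incident rate of 33 to 35% in the valganciclovir arm and 5 to 6% in the maribavir arm, 32 patients in each arm" are required for at least 80% power, two-sided alpha 0.05, "and using the chi square test". On dropout: "This sample-size will be inflated to 35 patients per arm to address an expected dropout/lost to follow-up rate of 3-5% in each arm". Section 6.0 confirms the design: "70 patients will be randomized 1:1 (35 in each arm) in blocks of 10".

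**The concern.** The covariate limit guards against too many parameters for the total number of events. The weak point here is a different one: the number of events in a single arm. If maribavir works as the plan expects, nearly all primary events fall in the valganciclovir arm, and the parameter that becomes unstable or inestimable is treatment itself. Dropping covariates cannot cure that.

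The better maribavir performs, the more likely the ordinary adjusted analysis is to break down. A report could then show a strongly positive unadjusted test beside an adjusted hazard ratio that is not estimable, or that carries a p-value near 1. In an open-label trial, a remedy chosen after seeing an empty arm would be open to criticism that a pre-specified one avoids.

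**Working it through.** **Inputs from the documents.** 35 patients per arm; 12-month follow-up; primary event rates of 33-35% (valganciclovir) and 5-6% (maribavir); two-sided alpha 0.05; required n of 32 per arm.

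**1. The plan's own figure.** For the least favourable pair, 33% vs 6%, the Pearson formula with pooled variance gives

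n = [1.96·√(2 × 0.195 × 0.805) + 0.842·√(0.33 × 0.67 + 0.06 × 0.94)]² / 0.27² = 32.6, so 33 per arm, against 32 stated.

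A likelihood-ratio chi-square calculation gives power 0.809 at 64 patients, exactly as in the plan's table. Dropout: 32/0.97 = 33.0 and 32/0.95 = 33.7, so 35 is enough. At 35 per arm the exact power of the Pearson test is 0.86 to 0.93 over the stated rates. The plan's sample size stands for the test it names.

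**2. Events in the maribavir arm.**
- Expected: 35 × 0.05 = 1.75; 35 × 0.06 = 2.10.
- Chance of none: 0.95^35 = 16.6%; 0.94^35 = 11.5%.

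**3. What an empty arm does to the Cox fit.** Let mᵢ and vᵢ be the numbers at risk in the maribavir and valganciclovir arms at the i-th event. With no maribavir events the log partial likelihood for treatment is −Σ log(mᵢ·e^β + vᵢ). It rises steadily as β goes to minus infinity, so there is no finite maximum. The hazard ratio runs to 0, its standard error diverges and the Wald p-value approaches 1. The likelihood itself stays bounded, with limit −Σ log vᵢ, so a likelihood-ratio test can still be computed.

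**4. Example: 12 events vs 0, 35 per arm, no earlier censoring.**
- Covariate limit: 12/5 = 2.4, so two covariates would be allowed.
- Ordinary Cox, Wald: p = 0.99, unbounded interval.
- Ordinary Cox, likelihood ratio: 2·Σ log[(70 − i)/(35 − i)] for i = 0 to 11 is 18.9 on 1 df, p < 0.001, but there is still no finite hazard ratio.
- Firth: hazard ratio 0.03 (95% CI 0.0003 to 0.25), p < 0.001.
- Fisher's exact test, unadjusted: p = 0.0002.

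**5. Power of the Cox analysis by test.** Simulation with exponential event times, censoring at 12 months, a treatment-only model, 35 per arm and 6,000 trials per row. Trials with no maribavir events count as no Wald rejection.

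| Valganciclovir vs maribavir | Wald | Likelihood ratio | Exact Pearson, for comparison |
|---|---|---|---|
| 33% vs 6% | 70% | 87% | 86% |
| 33% vs 5% | 68% | 90% | 90% |
| 34% vs 5% | 72% | 92% | 91% |
| 35% vs 5% | 73% | 93% | 93% |
| 35% vs 6% | 74% | 90% | 89% |

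Repeat simulations agree to within about 2 percentage points. Firth's method with the penalised likelihood-ratio test gives 92-93% at 35% vs 5% and 84-86% at 33% vs 6%. Its type I error is 4-5% with both arms at 20%. With 5% dropout, Wald power is 67-70%. Adding two covariates with assumed prevalences of 30% and 80% and no prognostic effect leaves it near 72%.

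**The case against.** **The 80% is not a claim about Cox regression.** A reader might infer that the trial's power is really about 70%, below what is stated. The documents do not support that. The 80% is for the unadjusted chi-square comparison, it reproduces, and that comparison remains in the plan. This part of the objection stands in full.

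**The plan does not name the Wald test.** Correct. The 68-74% applies only if the treatment effect is read from Wald output. The ordinary likelihood-ratio test loses nothing of note and does at least as well as Firth, so the power gain comes from leaving Wald and not from penalisation. But the plan does not name the likelihood-ratio test either, and that test alone still leaves no finite hazard ratio to report when an arm is empty.

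**The Cox model is conditional.** It is run only if necessary, and covariates are limited to those that differ significantly by arm. Under randomisation that is uncommon. With assumed prevalences of 20-50% for D+/R- and 60-90% for rATG, at least one of the two differs in 3-9% of trials; together with an empty maribavir arm, in about 0.4-1.5%. However, the same section also says that models will be adjusted for serostatus and rATG, which reads as routine adjustment, and it defines no trigger. How often the problem arises therefore depends on a choice the plan leaves open.

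**The rates may be higher.** The plan's table goes up to 10% in the maribavir arm. The chance of no events falls to 0.92^35 = 5.4% at 8% and 0.90^35 = 2.5% at 10%. That is fair, but 5-6% is the rate the plan itself adopts.

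**Aim 2.** A reader might infer that CMV disease will be equally sparse. The documents give no expected rate by arm. The one 12-month figure, 16.1%, is from D+/R- patients given 200 days of valganciclovir. Section 10.0 already concedes limited power for CMV infection.

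**Conclusion.** The gap is real but confined to the adjusted analysis. On the plan's own rates, about 1 trial in 6 (at 5%) to 1 in 9 (at 6%) would have no primary event in the maribavir arm. An ordinary Cox fit would then give no finite treatment hazard ratio, and the limit on covariates would not prevent it. If inference is by Wald statistics, power is about 70%, against 86-94% for likelihood-ratio inference on the same model.

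The event counts and zero-event probabilities follow from the documents alone. The power figures also assume exponential event times and 12-month administrative censoring, and the Wald figure assumes that default Wald output is used.

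The primary unadjusted comparison and its sample size are unaffected. This is an inexpensive improvement to the plan and does not correct its power statement.

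**What to change.** Add to the Statistical Methods that treatment inference in the Aim 1 Cox models, and in any Aim 2 Cox model with few or no events in an arm, will use Firth's penalised partial likelihood, with the penalised likelihood-ratio test and profile-likelihood confidence limits in place of Wald statistics. Put a number on few in advance; the plan's own figure of 5, counted per arm, would serve.

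The two parts do different jobs. Leaving Wald restores the power, and the penalisation supplies a finite hazard ratio with usable limits when an arm has no events.

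The cost is one sentence and the FIRTH option in SAS PROC PHREG, in software the plan already uses. No patients or data are added. The downside is slight shrinkage of the hazard ratio towards 1.
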